8.1.2. Postdiscontinuation Follow-Up Period Assessments

Postdiscontinuation short-term and long-term follow-up assessments will be conducted as described in the Study Schedule ([Attachment 1](#)). Adverse event (AE) information will be collected until at least 30 days after the last dose of study treatment. After the 30-day short-term follow-up visit, only new and ongoing SAEs deemed related to study treatment will be collected.

Long-term follow-up will continue as long as the patient is alive and has not withdrawn consent to follow-up or the study has completed (as defined in [Section 8.1.3](#)).

For patients who discontinue study treatment for any reason without objectively measured PD, imaging studies and tumor assessments are obtained every 6 weeks (± 7 days), irrespective of treatment cycles as calculated from randomization, until documented progression.

For patients that discontinue study treatment after objectively measured PD, the following information will be collected every 2 months (± 7 days) for the first 2 years, then every 6 months (± 14 days) until the patient's death, or overall study completion:

- details on all subsequent anticancer treatment (start/stop dates and treatments administered)
- first post-study treatment disease progression date
- survival status

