5.2.1.1. Efficacy Analysis Variables

Definition of efficacy analysis variables are listed.

Overall survival (OS) is defined for each patient as the time from the date of randomization to the date of death from any cause. If the patient is alive at the cutoff date for the analysis (or was lost to follow-up without a confirmed date of death), OS will be censored for analysis on the last date the patient was known to be alive.

Progression-free survival (PFS) is defined for each patient as the time from the date of randomization to the first date of radiologic disease progression (as defined by Response Evaluation Criteria In Solid Tumors, Version 1.1 [RECIST v.1.1]) based on investigator assessments or death due to any cause. [Table JGDJ.5.1](#) defines the rules of censoring to be applied to PFS. In addition, sensitivity analyses of PFS will be performed using different rules for censoring (as defined by [Table JGDJ.5.2](#)).

Table JGDJ.5.1. Censoring Rule of PFS Primary Analysis

Situation	Event / Censor	Date of Event or Censor
Tumor progression or death	Event	Earliest date of PD or death
No tumor progression and no death	Censored	Date of last adequate radiological assessment or date of randomization (whichever is later)
unless		
No baseline radiological tumor assessment available	Censored	Date of randomization
No adequate postbaseline radiological tumor assessment available and death reported after 2 scan intervals following randomization	Censored	Date of randomization
New anticancer treatment started and no tumor progression or death within 14 days	Censored	Date of adequate radiological assessment prior to (start of new therapy +14 days) or date of randomization (whichever is later)
Tumor progression or death documented immediately after 2 or more consecutive missing scan intervals following last adequate radiological tumor assessment or randomization (whichever is later)	Censored	Date of last adequate radiological assessment prior to the missing assessment or date of randomization (whichever is later)

Abbreviations: CR = complete response; PD = progressive disease; PR = partial response; SD = stable disease.

- a Symptomatic deteriorations (that is, symptomatic progressions, which are not radiologically confirmed) will not be considered as disease progressions.
- b Adequate radiological tumor assessment refers to an assessment with one of the following responses: CR, PR, SD, or PD.

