- c The 2-scan interval is counted from the date of last adequate tumor assessment to the date of next 2 scheduled tumor assessments plus 14 days (adjusted by tumor assessment window).
- d Refer to flow chart in [Appendix 1](#) if a patient meets multiple censoring criteria.
- e If there are multiple dates associated with 1 assessment, the assessment date will be set to the first date when the overall response is PD and the last date otherwise.

Table JGDJ.5.2. Censoring Rules for PFS Sensitivity Analysis Definitions

Sensitivity Analysis Definition #	Situation	Date of Progression or Censor	Censored / Progressed
SA 1: Count symptomatic deterioration as progression	Radiographic documented progression or symptomatic deterioration	Date of documented progression or date of symptomatic deterioration, whichever occurred first	Progressed
SA 2: Ignore new anticancer treatment	New anticancer treatment (systemic therapy) started before radiographic documented progression or death	A) Date of radiographic documentation of progression or death, whichever is earlier B) Last adequate radiological assessment if no radiographic documented progress or death occurred	A) Progressed B) Censored
SA 3: Ignore missing tumor assessment	Death or radiographic documented progression after ≥ 2 consecutively missed tumor assessment visits	Date of radiographic documentation of progression or death, whichever is earlier	Progressed
SA 4: Treat lost to follow up as progression	Patient is lost to follow-up without radiographic documented progression or death	Date of next scheduled postbaseline radiological assessment at or after becoming lost to follow-up	Progressed

Abbreviations: PFS = progression-free survival; SA = Sensitivity Analysis.

Progression-free survival 2 (PFS2) is defined as the time from the randomization date to the date of disease progression on next-line treatment, or death due to any cause, whichever occurs first. [Table JGDJ.5.3](#) defines the rules of censoring to be applied to PFS2. Note that disease progression on next-line treatment in this study will be recorded by investigators without details of corresponding radiologic assessment results. In the event that the date of disease progression on next-line treatment is reported only to the nearest month, the date will be imputed for analysis (assumed to have occurred on the 15th day of the reported month).

Table JGDJ.5.3. Censoring Rules of PFS2 Analysis

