PD on study therapy	Situation			Event / Censor	Date of Event or Censor
	PD after end of study therapy but prior to next line of treatment	PD on next line of treatment	Death		
Yes	No	Yes	Yes / No	Event	Event at PD date on next line of treatment
Yes	No	No	No	Censored	Censoring at the date PD-free on next line of treatment
Yes	No	No	Yes	1) Event 2) Censored	Event at death date if no further treatment, otherwise censoring at the date PD-free on next line of treatment
No	Yes	Yes	Yes / No	Event	Event at PD date on next line of treatment
No	No	Yes	Yes / No	Censored	Censoring at start of next line of treatment
No	Yes / No	No	No	Censored	Censoring at the date PD-free on next line of treatment
No	Yes	No	Yes	1) Event 2) Censored	Event at death date if no further treatment, otherwise censoring at the date PD-free on next line of treatment
No	No	No	Yes	Censored	Censoring at start of next line of treatment

Time to any progression (censoring for death without progression) is defined identically to PFS, except that the time to any progression will be censored at the date of death if there is no prior or concurrent radiologic disease progression. Otherwise, censoring follows the rules described in [Table JGDJ.5.1](#).

Time to any new metastasis (censoring for death and/or for progressive disease (PD) due to increased sum of target lesions) is defined for each patient as the time from the date of randomization to the first date of radiographic documentation of 1 or more new lesions. Time to any new metastases will be censored at the first date of radiologic disease progression if that progression was based solely on an increased sum of target lesions (without new lesions). If there is no radiologic disease progression, time to any new metastases will be censored following the rules of [Table JGDJ.5.1](#), with the exception that censoring will be applied at the date of death (if no previous event or censoring).

New-metastases-free survival (nMFS) is defined for each patient as the time from the date of randomization to the first date of radiographic documentation of 1 or more new lesions, or to the date of death from any cause (whichever occurs first). nMFS will be censored at the first date of radiologic disease progression if that progression was based solely on an increased sum of target lesions (without new lesions). Otherwise, nMFS will be censored for analysis in a manner analogous to PFS (following the rules of [Table JGDJ.5.1](#)).

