5.11.3.3. Analyses of Other Secondary Efficacy Variables

All time-to-event variables (including those defined in Sections [5.2.1.1](#) and [5.2.1.3](#)) will be analyzed using stratified log-rank tests (analogous to the primary analysis) for comparisons between study arms, stratified Cox models (for between-arm statistics including the treatment HR), and Kaplan-Meier method (for within-arm statistics).

Disease control (CR+PR+SD) rate will be reported along with exact confidence bounds (CI: 95%) and compared using the Cochran-Mantel-Haenszel test adjusting for the stratification variables.

Patient listings of tumor assessments (target and non-target lesion assessments and tumor response), OS, and PFS will be provided.

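### Time to any progression: a death without progression is censored at the death date even after scans have lapsed, so the progression-free proportion can be overstated; one qualifying phrase repairs it

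*SAP*

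**What the plan says.** SAP 5.2.1.1 defines time to any progression as PFS with one exception: "the time to any progression will be censored at the date of death if there is no prior or concurrent radiologic disease progression". It continues: "Otherwise, censoring follows the rules described in" Table JGDJ.5.1. The exception has one condition, the absence of radiologic progression. It does not ask when the last scan was or whether new therapy had begun.

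For PFS, Table JGDJ.5.1 treats a progression or death that follows two or more consecutive missing scan intervals as censored at: "Date of last adequate radiological assessment prior to the missing assessment or date of randomization (whichever is later". Other rows censor at randomization when there was no adequate post-baseline scan and death came more than two scan intervals later. They censor near the start of new anticancer therapy when neither progression nor death occurred within 14 days of it.

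Time to any new metastasis and time to progression by increased target-lesion sum also use the death date, but each follows Table JGDJ.5.1 "with the exception that censoring will be applied at the date of death (if no previous event or censoring".

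Protocol 8.1.2 requires that, after treatment stops without progression, "imaging studies and tumor assessments are obtained every 6 weeks" until progression is documented. SAP 5.11.3.3 analyses all time-to-event variables by stratified log-rank test, stratified Cox model and "Kaplan-Meier method (for within-arm statistics".

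**The concern.** A patient censored at death stays in the risk set, counted as progression-free, until the day of death. That is reasonable when the last clean scan was recent. It is not reasonable when scanning lapsed months earlier, because nobody knows whether the tumour had grown. The PFS rules guard against this, and the literal wording for time to progression removes the guard.

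The wording is also lopsided. A progression found after a long gap falls under the residual clause and is censored back to before the gap. A death after the same gap is carried forward to the death date. After identical gaps, the patient with a documented progression contributes less progression-free time than the patient who was never scanned again.

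At stake are the reported progression-free proportions and medians for a prespecified efficacy measure (Protocol 10.1.4). The missing-scan sensitivity analyses in Table JGDJ.5.2 are defined for PFS, and none is specified for this endpoint.

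**Working it through.** The plan states no figure for time to progression, so there is none to reproduce.

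**1. The rules side by side, for a death with no documented progression**

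| Situation | PFS (Table JGDJ.5.1) | Time to any progression, literal | Two neighbouring endpoints |
|---|---|---|---|
| Death after ≥2 missed scan intervals | Censored at last adequate scan | Censored at death | Table JGDJ.5.1 acts first |
| No adequate post-baseline scan, death after 2 intervals | Censored at randomization | Censored at death | Table JGDJ.5.1 acts first |
| New therapy, no progression or death within 14 days | Censored at the scan before (start + 14 days) | Censored at death | Table JGDJ.5.1 acts first |

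Only time to any progression lacks the qualifier.

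**2. Length of the gap that triggers the table.** The footnote says: "The 2-scan interval is counted from the date of last adequate tumor assessment to the date of next 2 scheduled tumor assessments plus 14 days". With 6-weekly scans this is 2 × 42 + 14 = 98 days, or 98/30.4375 = 3.2 months.

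**3. Direction.** The Kaplan-Meier estimate is S(t) = ∏(1 − d/n). Moving a censoring date from the last scan to a later death raises n at every event time in between and leaves d unchanged. So S(t) can only stay equal or rise.

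**4. Ten patients.** Eight progress at months 2, 4, 6, 8, 10, 12, 14 and 16. Two have a last clean scan at month 3 and die at month 15, a gap of 12 months, longer than 3.2.
- Literal rule: S(6) = 9/10 × 8/9 × 7/8 = 0.700; S(12) = 0.700 × 6/7 × 5/6 × 4/5 = 0.400.
- Table JGDJ.5.1 first: both leave at month 3, so S(6) = 9/10 × 6/7 × 5/6 = 0.643; S(12) = 0.643 × 4/5 × 3/4 × 2/3 = 0.257.

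**5. Illustration of size.** From the documents: 6-weekly scans, and the control-arm PFS median of 4.5 months (footnote to SAP Table JGDJ.5.5), used as a stand-in for time to progression. Assumed: exponential progression, detection at the next scan, end of scanning independent of progression, and an exponential time from then to death.

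The benchmark is complete scanning. The last scan before month 12 is the eighth, at 8 × 42/30.4375 = 11.04 months, so the observable proportion is exp(−ln 2 × 11.04/4.5) = 0.183.

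With scanning ending at 0.02 per month, about 13% of patients stop before detected progression. Simulating 400,000 patients gives these 12-month proportions:

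| Mean months from end of scanning to death | Literal rule | Table JGDJ.5.1 first |
|---|---|---|
| 3 | 0.204 | 0.186 |
| 6 | 0.221 | 0.186 |
| 10 | 0.231 | 0.184 |

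The excess over 0.183 is about 2 to 5 percentage points under the literal rule and at most about 0.3 with the table acting first. A second model sets 5-30% of patients to stop scans within the first 6 months, with mean gaps of 3-12 months to death. It gives an excess of about 0.5 to 11 points, and about 0.6 at most with the table first.

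**6. Between arms.** With the SAP's PFS medians (4.5 and 7.15 months) and equal gaps in both arms, the rate ratio moves from about 0.65 to between 0.65 and 0.71, toward 1. With identical progression but an assumed 15 versus 10 months of survival after scans stop, the hazard ratio is 0.95-0.97 instead of 1.

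**The case against.** The endpoint is introduced as identical to PFS apart from death becoming a censoring. One can read that as keeping every Table JGDJ.5.1 row and changing only the status of a death that would have been a PFS event. This may well be the intent, and the neighbouring definitions point the same way. But those definitions needed explicit words to say so, while here the table is invoked only for what the exception leaves over. Two programmers could derive different dates. The table's footnote refers multiple censoring criteria to the Appendix 1 flow chart, which is not visible in the text available. It is titled for PFS, and the exception for this endpoint does not cite it.

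Long gaps are also departures from the protocol. Scans continue until progression, and Protocol 8.1.1 asks for radiographic confirmation after symptomatic deterioration. The affected group could be small. This limits the size but does not remove the problem, since Table JGDJ.5.1 itself provides for missed scans and for therapy begun before progression.

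Three stronger readings are tempting and not supported:
- That the two lesion-type endpoints share the fault. They do not: death-date censoring applies there only "censoring will be applied at the date of death (if no previous event or censoring".
- That the bias should be measured against the latent 12-month proportion, exp(−ln 2 × 12/4.5) = 0.157. Progression can be seen only at scans, so about 2.5 points of that difference (0.183 − 0.157) come from scan timing and not from the rule.
- That the rule favours olaratumab. The direction depends on how post-scan survival differs between arms, and with equal gaps the ratio moves toward 1.

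**Conclusion.** The point holds as a defect in one sentence. Literally applied, the definition counts unscanned time, or time on later therapy, as progression-free for patients who die without documented progression, and the Kaplan-Meier proportion can then only be equal or too high. Under the main illustration the 12-month control-arm value is 20-23% instead of 18.3%. The stopping rates and survival gaps behind those figures are assumptions, because the documents give neither. Patients alive at the data cutoff fall under Table JGDJ.5.1 anyway, which would reduce the effect somewhat.

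The comparison with 18.3% also assumes that scanning stops for reasons unrelated to progression. If scans stop because progression is near, last-scan censoring is itself optimistic and death-date censoring more so. The repair does not cure that.

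A reader might infer a threat to the trial's main conclusions, but there is none. Time to any progression is an additional efficacy measure, is not a listed secondary objective, and lies outside the error-controlled set of OS, PFS and ORR (SAP 5.6).

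**What to change.** In SAP 5.2.1.1, qualify the death-date censoring in the definition of time to any progression with words such as *if no previous event or censoring under Table JGDJ.5.1*. The table then acts first, and the death date applies only to the remaining deaths, chiefly those within about 14 weeks of the last adequate scan. The two lesion-type endpoints need no change.

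The cost is one phrase. The censoring dates are already derived for PFS, so no new data or programming logic is needed. Censoring every death at the last adequate scan would also work but goes further than necessary; it could serve as a sensitivity analysis.

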9.6. Concomitant Therapy

All concomitant medications should be recorded throughout the patient's participation in the study.

Concomitant medications and supportive care therapies must also be documented at the time of discontinuation and at the 30-day short-term follow-up visit.

With the exceptions listed in the sections below, no other chemotherapy, investigational medications, other anticancer therapy, immunotherapy, hormonal cancer therapy, radiation, surgery for cancer, or investigational medications will be permitted while patients are on study treatment.

Biophosphonate osteoclast inhibitors (eg, zoledronic acid or pamidronate) for treatment of bone metastases will be permitted while patients are on study treatment. However, the osteoclast inhibitor denosumab is a monoclonal antibody and could confound safety analysis in the study if the patient experiences a hypersensitivity reaction to denosumab. Therefore, concomitant use of denosumab will not be permitted.

Appropriate documentation for all forms of premedications, supportive care, and concomitant medications (for example, medications such as sedatives, antibiotics, analgesics, antihistamines, corticosteroids, erythropoietin; procedures such as paracentesis, thoracentesis; or blood products such as blood cells, platelets, fresh frozen plasma transfusions) must be captured on the eCRF.

If doxorubicin premedication is required prior to the doxorubicin infusion, this must be done after the completion of olaratumab/placebo infusion, not before the olaratumab/placebo infusion.

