12.2.4.1. Postdiscontinuation Therapy

The numbers and percentages of patients reporting postdiscontinuation therapies will be provided overall, by type of therapy (surgery, radiotherapy, or systemic therapy), and by drug name, for the ITT population.

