Progressive Disease (PD): At least a 20% increase in the sum of the diameters of target lesions, taking as reference the smallest sum on study (including the baseline sum if that is the smallest). In addition to the relative increase of 20%, the sum must also demonstrate an absolute increase of at least 5 mm. The appearance of 1 or more new lesions is also considered progression.

For equivocal findings of progression (for example, very small and uncertain new lesions; cystic changes or necrosis in existing lesions), treatment may continue until the next scheduled assessment. If at the next scheduled assessment, progression is confirmed, the date of progression should be the earlier date when progression was suspected.

Stable Disease (SD): Neither sufficient shrinkage to qualify for PR nor sufficient increase to qualify for PD, taking as reference the smallest sum diameters while on study.

Not Evaluable: When an incomplete radiologic assessment of target lesions is performed or there is a change in the method of measurement from baseline that impacts the ability to make a reliable evaluation of response.

Evaluation of Nontarget Lesions

Complete Response: Disappearance of all nontarget lesions and normalization of tumor marker level. All lymph nodes must be non-pathological or normal in size (<10mm short axis).

Non-CR/ non-PD: Persistence of 1 or more nontarget lesions and/or maintenance of tumor marker level above the normal limits.

Progressive Disease: Unequivocal progression of existing nontarget lesions. The appearance of 1 or more new lesions is also considered progression.

Not Evaluable: When a change in method of measurement from baseline occurs and impacts the ability to make a reliable evaluation of response.

Evaluation of Best Overall Response

The best overall response is the best response recorded from the start of the study treatment until the earliest of objective progression or start of new anticancer therapy, taking into account any requirement for confirmation. The patient's best overall response assignment will depend on the findings of both target and nontarget disease and will also take into consideration the appearance of new lesions. The Best Overall Response will be calculated via an algorithm using the assessment responses provided by the investigator over the course of the trial.

Time Point Response

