It is assumed that at each protocol-specified time point, a response assessment occurs. (When no imaging/measurement is done at all at a particular time point, the patient is not evaluable (NE) at that time point.) Table 1 provides a summary of the overall response status calculation at each time point for patients who have *measurable disease* at baseline.

Table 1. Time Point Response: Patients with Target (\pm Nontarget) Disease

Target Lesions	Non-Target Lesions	New Lesions	Overall Response
CR	CR	No	CR
CR	Non-CR/non-PD	No	PR
CR	Not evaluated	No	PR
PR	Non-PD or not all evaluated	No	PR
SD	Non-PD or not all evaluated	No	SD
Not all evaluated	Non-PD	No	NE
PD	Any	Yes or No	PD
Any	PD	Yes or No	PD
Any	Any	Yes	PD

Abbreviations: CR = complete response; PR = partial response; SD = stable disease.; PD = progressive disease; NE = inevaluable.

Table 2 is to be used when patients have *nonmeasurable* disease only.

Table 2. Time Point Response: Patients with Nontarget Disease Only

Nontarget Lesions	New Lesions	Overall Response
CR	No	CR
Non-CR/non-PD	No	Non-CR/non-PD ^a
Not all evaluated	No	NE
Unequivocal PD	Yes or No	PD
Any	Yes	PD

Abbreviations: CR = complete response; PD = progressive disease ; NE = inevaluable.

^a non-CR/non-PD is preferred over SD for nontarget disease.

Frequency of Tumor Re-Evaluation

A baseline tumor evaluation must be performed within 4 weeks before patient begins study treatment. Frequency of tumor re-evaluation while on and adapted to treatment should be protocol-specific and adapted to the type and schedule of treatment. In the context of Phase 2 studies where the beneficial effect therapy is not known, follow-up every 6-8 weeks is reasonable. Normally, all target and non-target sites are evaluated at each assessment using the same method. However, bone scans may need to be repeated only when CR is identified in target disease or when progression in bone is suspected.

Confirmatory Measurement/Duration of Response

Confirmation:

The main goal of confirmation of objective response in clinical trials is to avoid overestimating the response rate observed.

In *randomized trial* (Phase 2 or 3) or studies where SD or progression is the primary endpoints, confirmation of response is not required.

In the case of SD, follow-up measurements must have met the SD criteria at least once after start of treatment at a minimum interval not less than 5 weeks measured from randomization..

Duration of Overall Response

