Time to any progression based solely on increased sum of target lesions is defined as the time from the date of randomization to the first date of radiologic disease progression based solely on an increased sum of target lesions. Time to progression based on an increased sum of

target lesions will be censored at the first date of radiologic disease progression if that progression was based solely on new lesions. If there is no radiologic disease progression, time to any progression based on an increased sum of target lesions will be censored following the rules of [Table JGDJ.5.1](#), with the exception that censoring will be applied at the date of death (if no previous event or censoring).

Objective response rate (ORR) is defined as the proportion of randomized patients achieving a best overall response of PR or CR per RECIST v.1.1. Patients who do not have any postbaseline tumor response assessments are considered non-responders and are included in the denominator when calculating the response rate. Tumor assessments performed after initiation of new anticancer treatment (systemic therapy) will be excluded from evaluating the best overall response.

Disease control rate (DCR) is defined as portion of randomized patients achieving a best overall response of CR, PR, or SD per RECIST v.1.1. Patients who do not have any postbaseline tumor response assessments for any reason are considered non-responders and are included in the denominator when calculating the response rate. Tumor assessments performed after initiation of new anticancer treatment (systemic therapy) will be excluded from evaluating the best overall response.

Duration of response (DoR) is defined for each patient with a best response of CR or PR as the duration from the first date of CR or PR to the first date of radiologic disease progression or death due to any cause. DoR will be censored according to the same rules as PFS.

Duration of Disease Control (DDC) is defined for each patient with a best response of CR, PR, or SD as the time from randomization to the first date of radiologic disease progression or death due to any cause. DDC will be censored according to the same rules as PFS.

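### The SAP's scan cut-off for best overall response names only systemic therapy, so responses first seen after off-study surgery or radiotherapy are not excluded from ORR and DCR

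*SAP*

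**What the plan says.** SAP 5.2.1.1 defines ORR and DCR as proportions of randomized patients by best overall response per RECIST 1.1. Both definitions carry the same cut-off: "Tumor assessments performed after initiation of new anticancer treatment (systemic therapy) will be excluded from evaluating the best overall response". Neither mentions surgery or radiotherapy.

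Protocol Attachment 6 (Evaluation of Best Overall Response) runs the window "until the earliest of objective progression or start of new anticancer therapy", with no systemic qualifier.

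The term also varies within SAP 5.2.1.1. The primary PFS rule in Table JGDJ.5.1, which also governs DoR and DDC, refers to new anticancer treatment without a qualifier. Sensitivity analysis SA 2 in Table JGDJ.5.2 restores it: "New anticancer treatment (systemic therapy) started before radiographic documented progression or death".

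Elsewhere the plan treats local therapy as its own category. Protocol 12.2.4.1 tabulates post-discontinuation therapy "by type of therapy (surgery, radiotherapy, or systemic therapy"), and SAP 5.12 does the same.

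**The concern.** ORR is hypothesis H3 in the alpha-controlled testing graph, and DCR is a secondary endpoint with the same cut-off. Both are meant to measure response to study treatment. If a target lesion shrinks or disappears because it was irradiated or removed after study drug stopped, a response recorded from that scan says nothing about olaratumab.

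Such responses in equal numbers in both arms leave the absolute difference unchanged but raise its variance. In unequal numbers they bias the difference, in either direction.

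DoR is also exposed, because it is censored by the PFS rules. If the response window and the PFS censoring rule use different meanings of new anticancer treatment, a patient's DoR could be censored before the response date.

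**Working it through.** **Can such a scan exist, and does the SAP keep it?**

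1. Protocol 9.6 and 9.6.2 bar radiation and cancer surgery during study treatment. Protocol 7.3.2 requires study drug to stop before another effective agent or procedure is introduced. Local therapy therefore follows discontinuation, which may occur without progression.
2. Scanning goes on. Protocol 8.1.2: "For patients who discontinue study treatment for any reason without objectively measured PD, imaging studies and tumor assessments are obtained every 6 weeks", until progression is documented. Protocol 10.1.2 agrees.
3. If no systemic therapy has started, the SAP cut-off has not been reached, so the scan remains eligible.
4. One scan is enough: under Attachment 6, for randomized trials, "confirmation of response is not required". The confirmed-response sensitivity analysis in SAP 5.11.3.2 (4-week interval) does not close the gap, because both scans can follow the local therapy. Independent review (Protocol 8.1.5) is optional and covers selected patients only.
5. The SAP text is what will be programmed. Protocol 10.1.4 assigns the specific definitions of these measures to the SAP, and Attachment 6 says best response is derived by algorithm from investigator assessments. Protocol 12.2.1 lets the SAP make minor modifications if they are described and justified. The SAP revision history gives no reason for a systemic-only limit.

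**Duration of response.** Table JGDJ.5.1 censors at an adequate scan before the start of new therapy plus 14 days. Suppose new therapy there includes local therapy, and a response is first seen on a scan more than 14 days after local therapy began. The censoring date then precedes the response date and DoR is negative. If Table JGDJ.5.1 means systemic therapy only, this does not happen.

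**Sensitivity of the ORR test (illustration).** The plan states no power for ORR, so there is no figure of its own to reproduce here. Its OS figures (322 events; 322/0.70 = 460 patients) do not use response data.

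Inputs from the documents: 230 patients per arm (SAP 5.1); response rates of 12% and 19% (footnote to SAP Table JGDJ.5.5). This gives 230 × 0.12 = 27.6 and 230 × 0.19 = 43.7, rounded to 28 and 44 responders. Assumed, because the documents give no rate: the number of extra responders created by local therapy.

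Unstratified approximation to the Cochran-Mantel-Haenszel test, with p̄ = (x₀ + x₁)/460:

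z = [(x₁ − x₀)/230] / √[p̄(1 − p̄) × 2/230]

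Base case: p̄ = 72/460 = 0.1565; standard error = √(0.1565 × 0.8435 × 2/230) = 0.0339; difference = 16/230 = 0.0696; z = 2.05; one-sided p = 0.020.

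| Extra responders (control, experimental) | Counts | One-sided p |
|---|---|---|
| 0, 0 | 28 v 44 | 0.020 |
| 2, 2 (0.9% of each arm) | 30 v 46 | 0.022 |
| 5, 5 (2.2%) | 33 v 49 | 0.026 |
| 10, 10 (4.3%) | 38 v 54 | 0.031 |
| 0, 5 | 28 v 49 | 0.004 |
| 5, 0 | 33 v 44 | 0.085 |

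The relevant level is 0.025 only when both OS hypotheses and PFS have been rejected. If ITT OS and PFS are rejected but LMS OS is not, Table JGDJ.5.5 gives ORR 0.00002, and no row comes near it.

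**The case against.** A reader might infer that the SAP credits shrinkage or removal of a lesion by local therapy as a response. The documents do not go that far. The SAP sentence is an exclusion rule. It fails to exclude such scans, but nothing says how a resected or irradiated target lesion is scored on study. At baseline, Attachment 6 treats irradiated or locally treated lesions as non-measurable unless they have progressed. That rule does not govern on-study scoring, but it makes automatic credit doubtful. The SAP also defines ORR per RECIST 1.1, and Attachment 6 may already close the window. What stands is a conflict between two documents, with the SAP as the operative text.

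It can also be argued that Attachment 6 leaves new anticancer therapy undefined, so the SAP merely clarifies it. Protocol 9.6 lists other anticancer therapy beside radiation and cancer surgery, which is weak support because the items in that list overlap. The plain wording is still broader than the SAP's, and both documents tabulate surgery and radiotherapy apart from systemic therapy.

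A reader might further infer that resection after down-staging is expected here. Protocol 5.1 makes that remark about doxorubicin with ifosfamide, a different regimen. Eligibility requires disease not amenable to curative surgery or radiotherapy, and exclusion criterion 20 removes patients with planned or required major surgery. A patient down-staged to surgery may also have responded beforehand. These points support a small number of cases.

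Nor is negative DoR certain. SA 2 is the counterpart of the Table JGDJ.5.1 rule, and its systemic qualifier suggests that the table means systemic therapy too. Leaving PFS uncensored at local therapy is then a legitimate treatment-policy choice.

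Finally, the trial is double-blind, and nothing in the documents predicts a difference between arms in local therapy. The one-sided rows of the table show sensitivity only.

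**Conclusion.** The point holds as a definitional conflict with a possible effect on an alpha-controlled endpoint. Programmed as written, the SAP does not exclude a partial or complete response first seen after off-study surgery or radiotherapy, provided the patient stopped study drug without progression and has not started systemic therapy. Protocol Attachment 6, on its plain wording, would end the window before that scan.

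The size is unknown. A case needs discontinuation without progression, local treatment of target lesions, no earlier response, a later scan, and an investigator assessment of response, so the number is probably small. The illustration shows that about five cases could matter if ORR is tested at 0.025. It rests on the SAP's design rates, an unstratified test and assumed counts, and is not an estimate of bias.

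OS, its event targets and the sample size are unaffected. ORR is the last hypothesis in the sequence, but ORR and DCR are planned efficacy results in their own right. The correction is worth making before unblinding because it is cheap and removes a judgment that would otherwise be made with results in view.

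**What to change.** 1. In the ORR and DCR definitions of SAP 5.2.1.1, replace the systemic-therapy qualifier with: systemic therapy, surgery for cancer, or radiotherapy to tumor lesions. This brings the cut-off into line with Attachment 6.
2. State in Tables JGDJ.5.1 and JGDJ.5.2 which meaning of new anticancer treatment applies to PFS. Whether PFS is censored at local therapy is the sponsor's choice; it should be explicit and used consistently.
3. Make sure DoR cannot be censored before the response date under the chosen definitions.
4. State how an on-study resected or irradiated target lesion is scored.
5. Confirm that the eCRF records dates of surgery and radiotherapy in patients who stop without progression. Protocol 8.1.2 and the Attachment 1 post-discontinuation schedule specify dated collection of subsequent treatment only for patients who stop after objective progression. Protocol 10.1.2, Protocol 12.2.4.1 and SAP 5.12 are broader but do not clearly fill that gap.

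The cost is SAP wording and programming, plus an eCRF clarification if the dates are not already captured. The downside is that a few patients may lose a late response that study treatment did produce.
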